3. TRIAL DESIGN

3.1. General Design

This is a two arm, multicentre phase III randomised trial of prophylactic anti-epileptic drug (Levetiracetam) versus no anti-epileptic drug (AED) (comparator) in patients with suspected cerebral glioma.

Randomly assigned - 1:1 basis

This will not be a blinded study and will not have placebo control and as such will be a "real world" study of prophylactic AED vs. no AED. The reasons for the lack of placebo arm include; real world nature of the study, patient involvement feedback on the design with specific reference to value of a placebo arm; over-encapsulation as levetiracetam capsules are large; and cost of the study.

804 patients will be recruited and randomised into one of two arms:

- **Group 1**: Levetiracetam 500mg twice daily for 2 weeks, then increasing to 750mg twice daily thereafter for 1 year. Patients should have a minimum of 2 doses of 500mg prior to surgery. (In those with moderate chronic kidney disease stage 3 estimated Glomerular Filtration Rate (eGFR 30-59 mL/min/1.73 m²) a starting dose of 250mg twice a day for 2 weeks, then increasing to 500mg twice a day thereafter).
- **Group 2**: no AED treatment (standard care)

3.2. Inclusion Criteria

- 1) Patients with suspected cerebral glioma on MRI
- 2) Capable of giving informed consent
- 3) Patients must be \geq 16 years old
- 4) Patients must have a Karnofsky performance status ≥70
- 5) Patients must be able to safely swallow pills
- 6) Planned surgery for presumed glioma (biopsy or resection)

3.4. Randomisation

After ensuring that the patients meet **all** eligibility criteria and has consented to participate in the study, sites will randomise the patient following the instructions described in the 'SPRING work instructions for sites.

Once a patient has been randomised, a patient study number will be issued and this should be used in all correspondence.

Informed Consent/Authorisation

All Patients that are eligible to receive therapy and randomised to AED arm must undergo an Electrocardiogram (ECG) and pregnancy test (if female and of child bearing age) prior to starting trial medication. AED arm patients must initiate treatment prior to surgery and have taken a minimum of two doses of 500mg Levetiracetam (two doses of 250mg in CKD3 patients) prior to surgery. See Patient Pathway (Page 7).

Prior to protocol enrolment and initiation of treatment, subjects must sign and date an approved consent form.

Eligibility Exceptions

Eligibility exceptions will not be granted.

Withdrawal of Subjects

Patients *discontinue* from the study drug for reasons such as safety or non-compliance. These patients will continue to be followed up for efficacy and safety as per protocol, unless they are lost to follow up or deceased. Patients may *withdraw* from the study at any point and they do not have to give a reason. However, we will ask the patient's permission to continue to collect information on their progress that is routinely recorded in their medical records. This is so that the overall quality of the study is not impaired. The patient can say no at this point and then no further data collection will take place, and will be censored at the point of withdrawal. This should be indicated on the case report form (CRF) as per completion guidelines.

Patients who consent to the trial but do not undergo planned surgery will be withdrawn from the trial. For any patient that did not undergo planned surgery, a further patient would be enrolled to the trial to maintain the target number of patients for analysis.

Please note that should it be medically required, participants in either study arm will be removed from the study and treated with appropriate medication according to standard care.

Patients on the levetiracetam arm who have prolonged QT as detected by pre-surgical ECG and QT interval ≥500milliseconds will not start taking levetiracetam. These patients will **not** be withdrawn but, a further patient would be enrolled to the trial to maintain the target number of patients for analysis

Criteria for Removal from Study Drug

- Patient wishes to come off levetiracetam.
- Unacceptable toxicity (as defined in Section 4.4)
- Seizure (as defined in Section 2.4). Where patients taking levetiracetam develop a seizure, they will stop taking the study drug and move to a prescribed treatment dose from the treating clinician, this will most likely be maybe a higher dose of levetiracetam. The patient may voluntarily withdraw from treatment at any time for any reason.
- Neurological progression e.g. development of dysphasia

- Pregnancy (all female patients of child bearing age on the levetiracetam arm will complete pregnancy testing prior to starting trial medication and will complete a pregnancy test at any time the patient confirms there is a possibility of pregnancy)
- Severe depression as defined by a PHQ-9 score of ≥20
- Suicidal ideation on interview.
- Prolonged QT (QT interval 2500milliseconds) as detected by ECG prior to surgery

NOTE: Unless the treating clinician advises an immediate stop of Levetiracetam for safety reasons, patients will be issued with a taper pack to minimise side effects.

4. TREATMENT

Drug Name: Levetiracetam

Supply: Levetiracetam tablets will be provided in 250 and 500mg strengths from UCB Pharma. Patients will be provided with an initial 4 month supply, followed by a three month supply at each clinic visit.

Dose:

Levetiracetam will be taken orally twice a day at approximately the same times each day, spaced as close to 12 hours apart as possible. Medication may be taken with or without food. Patients with impaired renal function (CKD 3, eGFR 30-59 ml/min/1.73m²) will have a different dose schedule consistent with the European levetiracetam label. All patients will start on a lower dose for the first 2 weeks and then titrate up as per Table 3 below. The aim of the dose titration is to reduce the side effects experienced by the patients.

Table 3 – Levetiracetam Dose Titration Schedule

| Normal treatment | Impaired Renal Function | |
|---|-------------------------|--|
| | treatment | |
| Randomisation-2 weeks | Randomisation-2 weeks | |
| 1 tablet of 500 mg AM | 1 tablet of 250 mg AM | |
| 1 tablet of 500 mg PM | 1 tablet of 250 mg PM | |
| Next 12 months | Next 12 months | |
| 1 tablet of 500 mg + 1 tablet of 250 mg = 750 mg AM | 1 tablet of 500 mg AM | |
| 1 tablet of 500 mg + 1 tablet of 250 mg = 750 mg PM | 1 tablet of 500 mg PM | |

Dose Reduction/Tapering:

Any patient reporting side effects from levetiracetam will be recorded and reported as per the Safety reporting section (section 5). Doses between 250mg bid or 750mg bid are permissible during the study. However, every effort should be made to maintain the target dose whenever possible. The treatment may be suspended, at the discretion of the treating investigator, however continuing therapy at a reduced dose should be seriously considered because of the risk of seizure associated with sudden cessation of any AED.

Once the patient has completed the trial at 12 months the hospital consultant/GP may recommend that the patient continues on this medication and if so they can arrange for it to be supplied on a prescription. All other patients should receive a dose reduction pack and the dose should be tapered according to Table 4 below:

Table 4 – Levetiracetam Dose Tapering Schedule

| Normal treatment | Impaired Renal Function |
|--|----------------------------------|
| | treatment |
| Week 1 | Week 1 |
| 1 tablet of 500 mg + 1 tablet of 250 mg = 750mg AM | 1 tablet of 500 mg = 500 mg AM |
| 1 tablet of 500 mg = 500 mg PM | 1 tablet of 250 mg = 250 mg PM |
| Week 2 | Week 2 |
| 1 tablet of 500 mg = 500 mg AM | 1 tablet of 250 mg = 250 mg AM |
| 1 tablet of 500 mg = 500 mg PM | 1 tablet of 250 mg $=$ 250 mg PM |
| Week 3 | Week 3 |
| 1 tablet of 500 mg = 500 mg AM | 1 tablet of 250 mg = 250 mg AM |
| 1 tablet of 250 mg = 250 mg PM | |
| Week 4 | No further treatment |
| 1 tablet of 250 mg = 250 mg AM | |
| 1 tablet of 250 mg = 250 mg PM | |
| Week 5 | No further treatment |
| 1 tablet of 250 mg = 250 mg AM | |
| Week 6 | No further treatment |
| No further treatment | |

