4.6. Drug Supplies and Labelling

The investigational product will be supplied by UCB Biopharma in blister packs. The investigational medicinal product (IMP) will be labelled and boxed and distributed to site for dispensing by site pharmacies. The patients will be provided with an initial 4 month supply at the Pre surgery (Baseline) visit followed by a three month supply at each scheduled clinic visit.

Details relating to IMP ordering and distribution can be found in the SPRING work instructions for sites.

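### Table 4 starts the 12-month taper at one fixed dose per renal group, so followed as written it raises the dose of completers already on a lower equal twice-daily dose

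*Protocol*

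**What the plan says.** All the governing text is in protocol section 4.

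- **Target dose (Table 3).** With normal renal function the maintenance dose is 750 mg twice daily; the morning dose is "1 tablet of 500 mg + 1 tablet of 250 mg = 750 mg AM", and the evening dose is the same. With impaired renal function it is 500 mg twice daily.
- **Reduced doses (Dose Reduction/Tapering).** "Doses between 250mg bid or 750mg bid are permissible during the study". Sites are told that "every effort should be made to maintain the target dose whenever possible". Where suspension is contemplated, "continuing therapy at a reduced dose should be seriously considered because of the risk of seizure associated with sudden cessation of any AED".
- **End of treatment.** After 12 months the consultant or GP may continue the drug on prescription. For everyone else: "All other patients should receive a dose reduction pack and the dose should be tapered according to Table 4 below".
- **Table 4.** There is one schedule for normal and one for impaired renal function. Each begins at a fixed dose.

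Two other places bear on the point. The note in section 3.4 on removal from study drug says that, unless an immediate stop is advised for safety, "patients will be issued with a taper pack to minimise side effects". Section 4.6 refers to a site document: "Details relating to IMP ordering and distribution can be found in the SPRING work instructions for sites".

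**The concern.** Section 4 foresees patients who reach 12 months below the target dose, yet the taper it prescribes is laid out only for patients on target. No sentence says where in Table 4 a patient on a reduced dose should begin. Such a patient, given the pack and following it from week 1, would take more levetiracetam than before.

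Section 4 introduces dose reduction in connection with side effects. The patients affected are therefore likely to include those who tolerated the drug poorly, and their dose would go up just when they are meant to be coming off it. Section 5.5 counts study treatment to the end of the taper medication, so this period falls within protocol treatment and safety reporting.

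**Working it through.** **Inputs.** Morning and evening doses in each Table 4 week; the permitted range (250 to 750 mg twice daily); the target doses in Table 3; and the supplied tablet strengths, 250 and 500 mg. All are from section 4.

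**Table 4 as daily totals (morning + evening, mg).**

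| Week | Normal | Impaired renal function |
|---|---|---|
| 1 | 750 + 500 = 1250 | 500 + 250 = 750 |
| 2 | 500 + 500 = 1000 | 250 + 250 = 500 |
| 3 | 500 + 250 = 750 | 250 |
| 4 | 250 + 250 = 500 | none |
| 5 | 250 | none |
| 6 | none | none |

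**On target, the table works.** Normal: 1500 to 1250 mg/day, a fall of 250/1500 = 17%. Renal: 1000 to 750 mg/day, a fall of 250/1000 = 25%.

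**On a lower equal twice-daily dose, it does not.** The tablets allow three such doses. Excess drug is the sum of (taper dose minus prior daily dose) x 7 over the weeks in which the difference is positive.

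| Prior dose | Weeks above prior dose (mg/day) | Ratio to prior dose | Week equal to prior dose | Days before first reduction | Excess (mg) |
|---|---|---|---|---|---|
| Normal, 500 mg bid (1000/day) | Week 1: 1250 | 1250/1000 = 1.25 | 2 | 14 | 250 x 7 = 1,750 |
| Normal, 250 mg bid (500/day) | Weeks 1-3: 1250, 1000, 750 | 2.5, 2.0, 1.5 | 4 | 28 | (750 + 500 + 250) x 7 = 10,500 |
| Renal, 250 mg bid (500/day) | Week 1: 750 | 750/500 = 1.5 | 2 | 14 | 250 x 7 = 1,750 |

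**Uneven doses.** The protocol does not say whether unequal morning and evening doses may be used as maintenance. If they are, a prior dose equal to the week 1 row (750/500 mg normal, 500/250 mg renal) is unchanged that week. A normal-renal patient on 500/250 mg (750 mg/day) would rise to 1250 and then 1000 mg/day, an excess of (500 + 250) x 7 = 5,250 mg.

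**How many patients.** The protocol gives no figure for completers on a reduced dose. Section 7.1 mentions a cited trial in glioma patients in which 21% reduced to 500 mg twice daily, but from a start of 1 g twice daily. That shows that reductions happen; it does not estimate their frequency at the lower doses used here.

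**The case against.** The strongest reply is that no sensible clinician would read the text this way. The subsection concerns reduction and tapering, and raising a dose is not tapering. Table 4 uses the same two column labels as Table 3, and its first row lies one 250 mg/day step below each target, so it reads naturally as the schedule for a patient on target. On that view only an entry rule is missing. Many clinicians probably would start lower down, and that part of the objection stands. But section 4.7 restricts the medication to use and dispensing as the protocol directs, so a sensible adaptation would depart from the text, while a site that followed the text would raise the dose.

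A second reply is that the site work instructions or the pack labels may give dose-specific directions. They are not available to check. Section 4.6 cites the work instructions for ordering and distribution, not for dosing. Even if they settle the matter, the dosing rule in the protocol should agree with them.

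Third, the largest figures belong to a normal-renal completer on 250 mg twice daily, and nothing shows how many of these there would be. That is correct, and the sizes above are per patient only. For 500 mg twice daily the increase is a single week at 250 mg/day extra.

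Fourth, the taper follows the 12-month visit and leaves the primary comparison of seizures within one year of randomisation (section 7.3.1) untouched. That is also correct, and it limits the weight of the point.

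**Conclusion.** The point holds. Read as written, Table 4 raises the daily dose for every equal twice-daily dose below target that the supplied tablets allow: by 25% for one week (normal, 500 mg), to between 2.5 and 1.5 times the prior dose over three weeks (normal, 250 mg), and by 50% for one week (renal, 250 mg). The first reduction is delayed by two to four weeks.

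The conclusion covers only 12-month completers who are tapered, not those continued on prescription. It assumes that the patient starts at week 1, as the text directs, and that no unseen site document overrides this. The effect is limited: no patient exceeds the target dose (1500 mg/day normal, 1000 mg/day renal), sites are asked to keep patients on target, and neither the sample size nor the primary analysis is affected. It is a dosing-safety defect that should be corrected, not a threat to the trial's main result.

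**What to change.** Add one sentence to section 4: patients enter Table 4 at the first step below their current daily dose. The entry points become:

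- normal, 750 mg bid: week 1 (1250 mg/day), as now
- normal, 500 mg bid: week 3 (750 mg/day)
- normal, 250 mg bid: week 5 (250 mg/day)
- renal, 500 mg bid: week 1 (750 mg/day), as now
- renal, 250 mg bid: week 3 (250 mg/day)

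No dose then rises, the weekly step stays at 250 mg/day, and the existing rows and tablets are used. The two lowest entries leave a single week at 250 mg/day before stopping. Because section 4 itself warns of seizures on sudden cessation, investigators should confirm clinically that this is long enough. If the taper pack in section 3.4 is the Table 4 pack, the same rule should apply there.

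The cost is the amendment wording and dose-specific pack instructions. No extra patients, visits or tablet strengths are needed. The make-up of the pack is not described, so the sponsor should check that it can be started part-way through.

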4.1. Pre-treatment Evaluation

General Requirements

- A history and neurological examination (to include demographic information and documentation of the Karnofsky Performance Status and Semantic Verbal Fluency Test (SVFT) shall be performed on all patients.
- 2) Documentation of tumour diagnosis on CT/MRI.
- 3) Blood test to confirm kidney function within the prior month as per routine pre-surgical blood screening
- 4) Patients will complete the pre surgery (baseline) assessments prior to the first dose of study medication at the clinic. At this time the assessments (PHQ-9, LAEP and EQ5D-5L) will be completed, by the patient, unless changes in vision or weakness make this difficult. If this occurs, then the carer or research nurse may read the questions to the patient or assist with marking the severity number or score as described by the patient. Proxy versions of EQ-5D-5L will also be available. Carers will also be asked to complete the Proxy version 1 of the EQ-5D-5L Questionnaire, this asks the carer how they would rate the patients health.

4.2. Treatment Schedule

Due to the nature of the trial, patients may present in two categories, those requiring urgent surgery (admitted to hospital, surgery within approximately 7 days) and those who will be outpatients awaiting an elective surgery date.

Outpatients may be seen prior to their pre-surgical visit, therefore the trial may be discussed with them during these appointments. If the treating clinician will not see the patient at a face-to-face visit, but instead have a telephone/video interview, prior to the pre-surgical visit, the patient informed consent may be posted to the patient to allow the patient additional time to consider participation. The full informed consent will be completed at the pre-surgical visit. The patients randomised to the levetiracetam arm will also leave the appointment with their initial levetiracetam supply to allow them to start the prophylactic treatment prior to surgery.

Inpatients may be in the position of requiring urgent surgery, the consent and randomisation may have to take place in a short period of time. Prior to randomisation, the trial team must ensure the patient has a minimum of 12 hours prior to surgery to allow for 2 doses of levetiracetam. Care will be taken by the trial team to allow for as much consideration time as possible prior to randomisation. If the patient does not feel able to make a decision with the time available to them they will be excluded from the trial.

Female patients of child bearing age randomised to the levetiracetam arm will be asked to complete pregnancy testing prior to starting medication. If they are pregnant, the patients will be withdrawn from IMP as per section 3.4.

Any patients randomised to the levetiracetam arm will receive an ECG prior to starting medication. Any patients who have prolonged QT as detected by pre-surgical ECG and QT interval ≥500milliseconds will not start taking levetiracetam as per section 3.4.

All patients will be monitored for clinical evidence of toxicity as described below

Unless otherwise noted, all evaluations may be performed within 14 days before the next scheduled clinic date.

- 1) All relevant information regarding drugs, doses, laboratory examinations, and treatment-related toxicities shall be documented in the patient's medical record and flow sheets.
- 2) A history and neurological exam (to include documentation of the patient's Karnofsky Performance Status, Semantic Verbal Fluency Test (SVFT)) and an Anterograde Memory test (Recall of a 7 item address after three attempts) will be performed at least every 3 months, +/-2 weeks.
- All patients will be followed for overall survival. Patients will be seen at 3 monthly clinic visits. In addition, all patient reported events will be recorded and safety reporting completed if required (Safety reporting detailed in section 5).

If patients have a seizure they will complete:

- Patient diary
- The Liverpool Impact of Epilepsy Scale (LIES) after first seizure then again one year after randomisation: this is used to assess the impact of epilepsy on a number of different aspects of daily life.
- The Liverpool Seizure Severity Scale (LSSS) will be completed after first seizure and again one year after randomisation.

The EQ5D-5L will be completed after first seizure.

4.3. Visit Schedule

Patient Visit Schedule

| | Screening / pre-surgery | Post- surgery | 3 month (+/- 2 wks) | 6, 9, 12 month (+/- 2 wks) | 18 month ^a (+/- 2 wks) | Reported suspected seizure |
|--|----------------------------|------------------|---------------------------|----------------------------------|--------------------------------------|----------------------------------|
| Written informed consent | х | | , | | | |
| Demographic data | х | | | | | |
| Medical /seizure history | х | | х | х | | |
| Concomitant medications | x | | х | x | S - details of AEDs only | |
| PHQ9 | Х | | Х | Х | | |
| Karnofsky Performance Status (Neurological exam) | х | | Х | x | | |
| Semantic Verbal Fluency Test (SVFT) (Neurological exam) | x | | х | x | | |
| Anterograde Memory test (Neurological exam) | x | | х | x | | |
| Tissue | S | | | | | |
| Blood (eGFR -kidney function) | S | | S | S | | |
| ECG ^d | x | | | | | |
| Pregnancy testing ^c | x | | | | | |
| Standard MRI imaging | S | S | S | | | |
| Liverpool Adverse Events Profile | x | | Х | x | | |
| EQ-5D-5L | x | | Х | х | | Х |
| Carer EQ-5D-5L | x | | Х | х | | |
| Liverpool Impact of Epilepsy Scale | | | | | | Х |
| Liverpool Seizure Severity Scale | | | | | | Х |
| Health Economic Questionnaire | x | | Х | x | | |
| Time & Travel Questionnaire ^b | | | | x | | |

^aFollow up will be every 3 months to at least one year after randomisation, where possible 18 month data will be collected until the end of trial ^bTime and Travel Questionnaire is at 6 month visit only ^c Pregnancy test should take place before first dose of IMP (if on IMP arm) ^dECG before first dose of IMP (if on IMP arm)

4.4. Treatment Breaks

- A 'treatment break' is a planned interruption to taking the study drug. If the treatment break is related to surgery, for example if the patient is admitted to a high dependency unit following surgery and unable to swallow the study drug then a treatment break of ≤14 days is permitted. The patient should then recommence study treatment at the prior treatment dose (starting dose) and escalate after that dose finishes. A scenario could be if the patient on the treatment arm is taking study drug for 4 days, then has a treatment break of 4 days post surgery, they will recommence on the starting dose for a further 10 days before escalating to the next dose. During a treatment break, standard of care treatment should be followed. This will not form part of the protocol. Following the recommencement of study drug the initial treatment dose.
- The clinician will be able to stop the study medication if they feel it is no longer safe for the patient to take tablets and the date of that decision will be recorded. In this instance, standard of care treatment should be followed. This will not form part of the protocol.
- Any treatment breaks should be recorded on the appropriate eCRF page.

4.5. Concomitant Therapy

Anti-tumour Treatment:

• Standard and experimental anti-tumour therapies are permitted.

Supportive Care:

- Dexamethasone should be used in the smallest dose to control symptoms of cerebral oedema and mass effect, and discontinued if possible.
- Febrile neutropenia may be managed according to the local institution's Infectious Disease guidelines. Measures may include appropriate laboratory testing, including blood and urine cultures and the institution of broad-spectrum antibiotics. If a source for the fever is not identified or the fever resolves when the neutrophil count recovers, antibiotics may be discontinued and the patient observed.
- The use of anti-emetics will be left to the investigators' discretion.
- Methotrexate use is an exclusion criteria and as such methotrexate should not be prescribed to patients enrolled in this trial. Where it is considered necessary to prescribe methotrexate patients should be removed from the trial.
- Therapies considered necessary for the wellbeing of the patient may be given at the discretion of the investigator. Other concomitant medications should be avoided except

for analgesics, chronic treatments for concomitant medical conditions, or agents required for life-threatening medical problems. All concomitant medications must be recorded.

